#### *11.4.1.17 Treatment of overdose*

An overdose is a dose in excess of the dose specified for each cohort in this CSP.

Over-dosing is not likely to occur in this study since all IMP will be administered by site personnel under medical surveillance. In cases of accidental overdose, standard supportive measures should be adopted as required.

An overdose should be documented as follows:

- An overdose with associated AE is recorded as the AE diagnosis/symptoms in the AE Log of the eCRF.
- An overdose without associated symptoms is only reported in the subject's medical records.

No known antidote is available.

#### 11.4.2 *Physical examination*

##### 11.4.2.1 *Full physical examination*

A complete physical examination will include assessments of the head, eyes, ears, nose, throat, skin, thyroid, neurological, lungs, cardiovascular, abdomen (liver and spleen), lymph nodes and extremities.

The result of the examination will be documented in the eCRF as normal, abnormal not clinically significant (NCS) or abnormal clinically significant (CS). Post-dose physical examination judged as abnormal CS will be reported as AE.

For timing of the assessments, refer to Table 8.1-1 and Table 8.1-2.

##### 11.4.2.2 *Brief physical examination*

A short version of physical examination will include an assessment of selected body systems at the judgement of the Investigator but will at least include cardiovascular, lung and abdomen.

The result of the examination will be documented in the eCRF as normal, abnormal NCS or abnormal CS. Post-dose physical examination judged as abnormal CS will be reported as AE.

For timing of the assessments, refer to Table 8.1-1 and Table 8.1-2.

#### 11.4.3 *Vital signs*

Systolic and diastolic blood pressure (BP) and pulse will be measured in supine position after 10 minutes of rest.

Vital signs will be judged as normal, abnormal NCS or abnormal CS. The assessment will be recorded in the eCRF. Post-dose vital signs judged as abnormal CS will be reported as AEs.

For timing of the assessments, refer to Table 8.1-1 and Table 8.1-2.

#### 11.4.4 *Body temperature*

Body temperature will be measured orally using a digital thermometer, and will be judged as normal, abnormal NCS or abnormal CS.

For timing of the assessments, refer to Table 8.1-1 and Table 8.1-2.

#### 11.4.5 *Resting 12-lead ECG*

Single 12-lead ECG will be recorded in supine position after 10 minutes of rest using an ECG machine. HR and PR, QRS, QT and QTcF intervals will be recorded.

Safety ECGs will be reviewed and interpreted on-site by the Investigator.

Any abnormalities will be specified and documented in the eCRF as NCS or CS. Abnormal post-dose findings assessed by the Investigator as CS will be reported as AEs.

For timing of the assessments, refer to Table 8.1-1 and Table 8.1-2.

#### 11.4.6 *Laboratory safety assessments*

Blood samples for analysis of clinical chemistry and haematology parameters will be collected through venepuncture or an indwelling venous catheter and sent to the certified clinical chemistry laboratory at Uppsala University Hospital and analysed by routine analytical methods.

Urine analysis will be performed at the research clinic using dip sticks. The assessments will be performed at visits specified in Table 8.1-1.

Urine pregnancy tests will be performed at visits specified in Table 8.1-1.

The safety laboratory parameters are defined in Table 11.4-1 and will be assessed at timepoints detailed in Table 8.1-1.

Safety laboratory parameters will be judged as normal, abnormal NCS or abnormal CS.

Abnormal values assessed by the Investigator as CS will be reported as AEs. If an abnormal value is associated with corresponding clinical signs or symptoms, the sign/symptom should be reported as the AE.

Table 11.4-1 Safety laboratory parameters

Category	Parameter
Clinical chemistry	Alanine aminotransferase (ALT)
	Albumin
	Alkaline phosphatase (ALP)
	Aspartate aminotransferase (AST)
	Bilirubin (total and conjugated)
	C-reactive protein (CRP)
	Calcium
	Creatinine
	Cystatin C
	Glucose
	Potassium
	Sodium
	Urea
Haematology	Haematocrit
	Haemoglobin (Hb)
	Platelet count
	Red blood cell (RBC) count
	White blood cell (WBC) count with differential count
Urinalysis (dip stick)	Bilirubin
	Erythrocytes
	Glucose
	Ketones
	Leucocytes
	Nitrite
	pH
	Protein
	Specific gravity
Urobilinogen	
FSH-test 	FSH
Pregnancy test 	Serum pregnancy test at screening
	Urine pregnancy test

 At screening only

 At screening, post-menopausal females only.

 Females only.

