#### 9.8.3 *Liver chemistry withdrawal criteria*

Liver chemistry threshold stopping criteria have been designed to assure subject safety and to evaluate liver event aetiology. Study treatment will be stopped if any of the following liver chemistry stopping criteria, defined in the U.S. Food and Drug Administration (FDA) Guidance on Drug-Induced Liver Injury [16], is met:

- Alanine aminotransferase (ALT) 3 x Upper Limit of Normal (ULN) and total bilirubin  $\geq 2xULN$  (>35% direct bilirubin); **or** ALT 3xULN and INR > 1.5)

*NOTE: plasma bilirubin fractionation will be performed. Bilirubin is also measured via urine dipstick (a measurement of direct bilirubin, which would suggest liver injury).*

- ALT 5xULN.
- ALT 3xULN if associated with symptoms (new or worsening) believed to be related to hepatitis (such as fatigue, nausea, vomiting, right upper quadrant pain or tenderness or jaundice) or believed to be related to hypersensitivity (such as fever, rash or eosinophilia).
- Subjects with ALT 3xULN **and** < 5xULN **and** bilirubin < 2xULN, who do not exhibit hepatitis symptoms or rash, will be allowed to continue study treatment as long as they are monitored weekly for four weeks.

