### **17.6.4 Body temperature**

Body temperature will be summarised. Data will be presented with absolute and percent change from baseline at each visit.

All data will be listed by subject.

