8.4.1.3 Vital signs

This section refers to secondary objective #1 and endpoint 1.2.

Vital signs (systolic/diastolic BP, pulse) and body temperature will be summarised. Data will be presented with absolute and percent change from baseline at each visit. Clinical evaluation of vital signs will be summarised in frequency tables.

All data will be listed by subject. See tables and listings in the statistical output layout, section 14.

8.4.1.4 *ECG resting 12-lead*

This section refers to secondary objective #1 and endpoint 1.2.

All ECGs will be categorised as “normal”, “abnormal, not clinically significant”, or “abnormal, clinically significant” (as judged by the investigator) and summarised using frequency tables. Changes over time will be presented using shift tables, if considered applicable.

All data will be listed by subject. See tables and listings in the statistical output layout, section 14.

8.4.1.5 *Safety laboratory analyses*

This section refers to secondary objective #1 and endpoint 1.2.

Safety laboratory data will be summarised with absolute and percent change from baseline at each visit. Abnormal, clinically significant values will be summarised separately if considered appropriate.

All data will be listed by subject. See tables and listings in the statistical output layout, section 14.

8.5 **Sensitivity analysis**

No sensitivity analyses are planned to be performed.

8.6 **Supplementary analyses**

No supplementary analyses are planned to be performed.

8.7 **Tertiary/exploratory endpoint(s) analysis**

Not applicable.

8.8 **Discontinuation**

Patients who discontinue from IMP treatment will be tabulated. The reason for discontinuation will be given. For discontinuation due to AE, the AEs will be given.

8.9 **Other analyses**

Not applicable.

8.10 **Interim analysis**

Not applicable.

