Assessment	Assessment timepoint	Result	Formulation A/B		
			Formulation A	Formulation B	Formulation A/B
[Parameter 1]	[Assessment timepoint 1]	[RESULT 1]	x(x.x%)/X	x(x.x%)/X	x(x.x%)/X
		[RESULT 2]	x(x.x%)/X	x(x.x%)/X	x(x.x%)/X
	[Assessment timepoint 2]	[RESULT 1]	x(x.x%)/X	x(x.x%)/X	x(x.x%)/X
		[RESULT 2]	x(x.x%)/X	x(x.x%)/X	x(x.x%)/X

Data based on [ANALYSIS SET].
 [STUDYID] [DOMAIN]: [PARAMETER CATEGORY], SAS program: descriptive_stat_tables.sas. Run by: [USERNAME], [USER EMAIL] [TIMESTAMP]

Table 14.3.x.x. ECG – shift table (analysis set)

Assessment	Assessment timepoint	Result	NORMAL	ABNORMAL CS	ABNORMAL NCS	MISSING	TOTAL
			n (%)	n (%)	n (%)	n (%)	n (%)
[Parameter 1]	[Assessment timepoint 1]	NORMAL	X (X%)	X (X%)	X (X%)	X (X%)	X (X%)
		ABNORMAL CS	X (X%)	X (X%)	X (X%)	X (X%)	X (X%)
		ABNORMAL NCS	X (X%)	X (X%)	X (X%)	X (X%)	X (X%)
		MISSING	X (X%)	X (X%)	X (X%)	X (X%)	X (X%)
		TOTAL	X (X%)	X (X%)	X (X%)	X (X%)	X (X%)

Data based on [ANALYSIS SET].
 [STUDYID] [DOMAIN]: [PARAMETER CATEGORY], SAS program: descriptive_stat_tables.sas. Run by: [USERNAME], [USER EMAIL] [TIMESTAMP]

Table 14.3.x.x. Safety laboratory results (analysis set)

[Parameter 1] (unit)	Result Category	Assessment timepoint	Formulation A/B		
			Formulation A	Formulation B	Formulation A/B fed
[Assessment timepoint 1]	Measured value	n	x	x	x
		Mean (SD)	x.xxx (x.xxx)	x.xxx (x.xxx)	x.xxx (x.xxx)
		Median (Min, Max)	x.xxx (x.xx, x.xx)	x.xxx (x.xx, x.xx)	x.xxx (x.xx, x.xx)
[Assessment timepoint 2]	Measured value	n	x	x	x
		Mean (SD)	x.xxx (x.xxx)	x.xxx (x.xxx)	x.xxx (x.xxx)
		Median (Min, Max)	x.xxx (x.xxx, x.xxx)	x.xxx (x.xx, x.xx)	x.xxx (x.xx, x.xx)
Absolute change from baseline	[Assessment timepoint 2]	n	x	x	x
		Mean (SD)	x.xxx (x.xxx)	x.xxx (x.xxx)	x.xxx (x.xxx)
		Median (Min, Max)	x.xxx (x.xxx, x.xxx)	x.xxx (x.xx, x.xx)	x.xxx (x.xx, x.xx)
Relative change from baseline (%)	[Assessment timepoint 2]	n	x	x	x
		Mean (SD)	x.x (x.x)	x.xxx (x.xxx)	x.xxx (x.xxx)
		Median (Min, Max)	x.x (x, x)	x.xxx (x.xx, x.xx)	x.xxx (x.xx, x.xx)

Data based on [ANALYSIS SET].
 [STUDYID] [DOMAIN]: [PARAMETER CATEGORY], SAS program: descriptive_stat_tables.sas. Run by: [USERNAME], [USER EMAIL] [TIMESTAMP]

Clinical chemistry, haematology, coagulation, and urinalysis

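### The SAP's only laboratory table applies means and percent change to dip-stick urinalysis, against its own rule for categorical data, and no table guarantees a count of new positives by treatment

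*Protocol*

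**What the plan says.** **How urine is tested.** Protocol 11.4.6: "Urine analysis will be performed at the research clinic using dip sticks". Table 11.4-1 lists ten items: bilirubin, erythrocytes, glucose, ketones, leucocytes, nitrite, pH, protein, specific gravity and urobilinogen.

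**How each result is classified.** The same section says "Safety laboratory parameters will be judged as normal, abnormal NCS or abnormal CS", and then "Abnormal values assessed by the Investigator as CS will be reported as AEs".

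**How results are summarised.** SAP 8.4.1.5: "Safety laboratory data will be summarised with absolute and percent change from baseline at each visit". Protocol 17.6.6 has the same sentence. Both leave a separate summary of clinically significant values to discretion. The only laboratory shell in SAP section 14.1 has rows for n, mean (SD) and median (min, max), for the measured value, the absolute change and the relative change in percent. The line below it reads "Clinical chemistry, haematology, coagulation, and urinalysis".

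**The general rule.** Protocol 17.1 and SAP 5.4 present categorical data as frequencies and percentages.

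**Baseline.** Protocol 17.1 takes the last value before each administration. SAP 5.3 takes the last value before the first dose only.

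**The concern.** The specific laboratory text and its shell treat a mainly categorical panel as continuous, while the general rule in both documents says otherwise. A programmer who follows the shell will produce means of grade codes and a percent-change row that is empty for exactly the subjects of interest. No urinalysis frequency table and no laboratory shift table is specified, although the SAP provides a frequency summary and a shift layout for ECG categories on the same three-level scale.

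Clinically significant change in safety laboratory parameters is a secondary endpoint. The non-clinical summary (protocol 6.1.5) says that the liver and biliary findings in dogs set the limits for human exposure. A note to protocol 9.8.3 adds: "Bilirubin is also measured via urine dipstick (a measurement of direct bilirubin, which would suggest liver injury". The natural group summary is therefore how many subjects turned positive on each treatment, and the plan does not guarantee it.

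**Working it through.** The plan states no figure to reproduce, so the check applies the shell's own statistics to simple cases.

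**Inputs from the documents.** 14 subjects included (SAP 4.4); 12 as the minimum evaluable number (protocol 9.3).

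**Assumptions.** The documents give neither a reading scale nor a coding. I take pH and specific gravity as numeric and the other eight items as graded or positive/negative. Negative is coded 0 and all subjects are negative at baseline. The codes 0 to 3 and 0/17/50/100 for negative, 1+, 2+ and 3+ are illustrative.

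**Formulas.** Absolute change = post − baseline. Percent change = 100 × (post − baseline) / baseline.

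| Case | Percent change defined for | Mean absolute change | Median | Min, max | Count table |
|---|---|---|---|---|---|
| n = 14, one new positive coded 1 | 0 of 14 (13 are 0/0, one is 1/0) | 1/14 = 0.071 | 0 | 0, 1 | 1/14 = 7.1% |
| n = 12, one new positive coded 1 | 0 of 12 (11 are 0/0, one is 1/0) | 1/12 = 0.083 | 0 | 0, 1 | 1/12 = 8.3% |
| n = 14, two at 2+, codes 0 to 3 | 0 of 14 | (2 + 2)/14 = 0.29 | 0 | 0, 2 | 2/14 = 14.3% |
| n = 14, two at 2+, codes 0/17/50/100 | 0 of 14 | (50 + 50)/14 = 7.1 | 0 | 0, 50 | 2/14 = 14.3% |

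In the first two rows the SD of the absolute change is √(1/n): 0.267 for n = 14 and 0.289 for n = 12.

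Three things follow.

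1. The percent-change failure does not need every baseline to be negative. A new positive is by definition negative at baseline, so with negative coded 0 it never enters that row. Recoding does not rescue the statistic: with negative = 1, a positive coded 2 gives 100 × (2 − 1)/1 = 100%, and the same positive coded 3 gives 200%.
2. The same clinical result gives a mean change of 0.29 or 7.1, depending only on the code.
3. Median, minimum and maximum do not count events. With 14 subjects the median averages the 7th and 8th ordered values, so anything from 1 to 6 positives at one grade (7.1% to 6/14 = 42.9%) gives the same median of 0, the same minimum and the same maximum.

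**The case against.** The strongest reply is that nothing is hidden and that the general rule already covers the case. Much of this stands.

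- A reader might infer that the plan cannot show a new positive at all. The documents do not support that. All laboratory data are listed by subject, with separate listings of laboratory values (16.2.13.1) and abnormal values (16.2.13.2), which are easy to read with 14 subjects. Clinically significant results become adverse events, and those are tabulated by treatment with n (%). If grades are coded, the maximum of the absolute change also shows that some positive occurred.
- A reader might infer that the secondary endpoint goes unreported. It concerns clinically significant changes, and those have the adverse-event route.
- A reader might infer that liver monitoring is weakened. The note on dip-stick bilirubin belongs to criteria for individual subjects, not to a group summary. ALT, AST, ALP and total and conjugated bilirubin are quantitative blood tests that the continuous shell suits.
- The shell looks like a template: its entries are placeholders, and its scope line names coagulation, for which Table 11.4-1 shows no parameter. Neither document says that a shell overrides the rule for categorical data.

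Three things remain. The general rule and the specific text point in different directions, and neither is given precedence. The separate summary of clinically significant values is optional. Positives judged not clinically significant reach no count by treatment, only listings.

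**Conclusion.** The point holds as a minor inconsistency with a practical consequence. The specific laboratory text and shell prescribe a method that does not suit categorical dip-stick items and that conflicts with the plan's own general rule. As a result, no specified table guarantees the number of new positives by treatment. It is not an absence of any rule for categorical data, and it is not a loss of data.

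Mean, SD and change remain workable for urine pH and specific gravity. The primary pharmacokinetic analysis is unaffected. The conclusion assumes that the other eight items are recorded as grades or positive/negative. The undefined percent change further assumes that negative is coded zero; under any other code the figure exists but is arbitrary. The numerical cases are illustrations, not forecasts of how many positives will occur.

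**What to change.** Change the SAP only; protocol section 17 leaves technical detail to it.

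1. In SAP 8.4.1.5 and the laboratory shell, restrict mean, SD, absolute change and percent change to numeric variables: clinical chemistry, haematology, and urine pH and specific gravity.
2. For the categorical dip-stick items, report n (%) in each result category by treatment and visit.
3. Add a shift table for those items, from the pre-dose (Day -1) result of each period to the 48 h result, reusing the ECG shift layout.
4. State that baseline for this table is per period, as in protocol 17.1. Under SAP 5.3 as written, a positive that first appears after Formulation A and persists would count as a change in the later periods too.
5. Record the departure from the wording of protocol 17.6.6 under SAP section 9.

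The cost is a few lines of SAP text and one reused table program. The results are already scheduled on Day -1 and at 48 h of each period (protocol Table 8.1-2), so no new data are needed and subjects are not affected.

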## 11.5 Appropriateness of measurements

All methods used for safety assessments are commonly used in standard medical care and in Phase I clinical studies. Non-compartmental analysis (NCA) of PK parameters is standard for Phase I clinical studies.

## **12 PROCEDURES FOR BIOLOGICAL SAMPLES**

### **12.1 Sample collection**

The sample collection procedure for PK analysis is described in Section 11.3.1.

Safety laboratory samples are collected according to standard procedures.

### **12.2 Volume of blood**

The estimated volume of blood to be collected from each subject during the study will be approximately 300 mL in Part I and Part II together. The anticipated volume of blood samples collected during the study from each subject will not exceed 450 mL (*i.e.*, less than the volume drawn during a regular blood donation).

### **12.3 Handling, storage and destruction of laboratory samples**

All biological samples will be registered in a biobank at CTC (893).

Any remains from the safety laboratory samples will be disposed of after analyses.

The samples for analyses of PK parameters will be stored at  $<-70^{\circ}\text{C}$  until analysed. The samples will be disposed of after the CSR has been finalised.

### **12.4 Chain of custody of biological samples**

A full chain of custody is maintained for all samples throughout their lifecycle.

CTC keeps full traceability of collected biological samples from the subjects while in storage at the research clinic until shipment and keeps documentation of receipt of arrival.

The sample receiver (the analytical laboratory) keeps full traceability of the samples while in their storage and during use until used or disposed of.

The Sponsor keeps oversight of the entire life cycle through internal procedures, monitoring of study sites and auditing of external laboratory providers.

### **12.5 Withdrawal of informed consent for donated biological samples**

If a subject withdraws consent to the use of biological samples donated, the samples will be disposed of/destroyed, if not already analysed and documented.

The Principal Investigator will ensure that:

- Subject withdrawal of informed consent is notified immediately to Sponsor.
- Biological samples from the subject, if stored at the research clinic, are immediately identified, disposed of/destroyed and the action is documented.

The Sponsor has to ensure that the laboratory(ies) holding the samples is/are informed about the withdrawn consent immediately and that samples are disposed of/destroyed or returned to the research clinic and the action is documented.

## **13 QUALITY MANAGEMENT, QUALITY ASSURANCE AND QUALITY CONTROL**

### **13.1 Quality management: critical process, system and data identification**

During CSP development, the Sponsor will identify those processes, systems (facilities, computerised systems) and data that are critical to ensure human subject protection and the reliability of trial results according to applicable SOPs and International Council for Harmonisation (ICH) E6 R2.

Identified risks will be categorised separately from the CSP.

### **13.2 Quality assurance and quality control**

The Sponsor is responsible for implementing and maintaining quality assurance (QA) and quality control (QC) systems with written SOPs with regards to management of identified risks, CSP compliance, good clinical practice (GCP) compliance and applicable regulatory requirements.

The Sponsor is responsible for securing agreements with involved subcontractors and to perform regular subcontractor oversight to ensure CSP compliance, GCP compliance and compliance with applicable regulatory requirements.

The Sponsor is responsible for implementing a risk-based validated electronic data capture system and maintain SOPs for the whole life cycle of the system.

QC should be applied to each stage of data handling to ensure that all data are reliable and have been processed correctly.

The Sponsor has delegated the responsibilities outlined above to CTC whilst maintaining overall study oversight.

## **14 ETHICAL AND REGULATORY REQUIREMENTS**

### **14.1 Ethical conduct of the study**

The study will be performed in accordance with ethical principles that have their origin in the Declaration of Helsinki [19] and are consistent with ICH GCP E6 (R2), EU Clinical Trials Directive, and applicable local regulatory requirements.

### **14.2 Ethics and regulatory review**

The Principal Investigator is responsible for submission of the CSP, the subject information and ICF, any other written information to be provided to the subjects and any advertisements used for recruitment of subjects to applicable IEC for approval.

The Sponsor has delegated to CTC the responsibility to submit study documents to the applicable CA according to local regulatory requirements.

Approval must be obtained in writing from both IEC and CA before the first subject can be recruited.

The Sponsor will provide the CA, IEC and Principal Investigators with safety updates/reports according to local requirements. Progress reports and notifications of SUSARs will be provided to the IEC according to local regulations and guidelines.

### **14.3 Subject information and consent**

It is the responsibility of the Investigator or an authorised associate to give each potential study subject adequate verbal and written information before any study specific assessments are performed.

The information will include the objectives and the procedures of the study as well as any risks or inconvenience involved. It will be emphasised that participation in the study is voluntary and that the subject may withdraw from participation at any time and for any reason, without any prejudice. All subjects will be given the opportunity to ask questions about the study and will be given sufficient time to consider participation before signing the ICF.

Before performing any study-related procedures the ICF must be signed and personally dated by the subject and by the Investigator. A copy of the subject information including the signed ICF will be provided to the subject.

Documentation of the discussion and the date of informed consent must be recorded in the source documentation and in the eCRF. The subject information sheet and the signed ICF should be filed by the Investigator for possible future audits and/or inspections.

The final approved version of the subject information and ICF must not be changed without approval from the Sponsor and the applicable IEC.

